18.3 Viral Status Information

HBV STATUS BASED ON HBV TEST RESULTS

Results of Standard Tests			HBV Status
HBsAg	anti-HBc	anti-HBs	
Positive	Positive	Negative	Positive (chronic infection)*
Positive	Negative	Negative	Positive (chronic infection)
Negative	Positive	Positive	Positive (past HBV exposure, now immune)**
Negative	Positive	Negative	Positive (chronic infection or past HBV exposure)**
Negative	Negative	Positive	Negative (prior vaccination, now immune)
Negative	Negative	Negative	Negative

* At high risk for HBV reactivation due to chemotherapy. Consider ordering confirmatory HBV DNA.

** At risk for reactivation due to chemotherapy, although risk is lower than those who are HBsAg-positive. Consider ordering confirmatory HBV DNA.

Three HBV screening tests should be done to determine HBV status: **HBsAg**: hepatitis B surface antigen; **anti-HBc**: antibody to hepatitis B core antigen (total Ig or IgG, but not IgM only); **anti-HBs**: antibody to hepatitis B surface antibody.

Refer to protocol [Section 10.2a](#) for the definition for HBV reactivation.

HCV STATUS BASED ON HCV TEST RESULTS

Results of Standard Tests		HCV Status
anti-HCV Screening Test (CIA or EIA)	anti-HCV Confirmatory Test (HCV RNA)	
Positive	Detectable	Positive (active infection)
Positive	Not detectable	Negative (prior infection)
Negative	Not needed	Negative

CIA: chemiluminescence immunoassay; **EIA**: enzyme immunoassay.

HIV STATUS BASED ON HIV TEST RESULTS

Results of Standard Tests		
Antibody OR combination Antigen and Antibody Test (Rapid HIV Antibody, EIA or ELISA)	Western Blot Confirmatory Test	HIV Status
Positive	Positive	Positive
Positive	Negative	Negative*
Negative	Not needed	Negative*

Rapid HIV antibody test: dot blot or immunoblot; **EIA:** enzyme immunoassay; **ELISA:** enzyme-linked immunosorbent assay; **PCR:** *Polymerase Chain Reaction*.

* If the patient is suspected to have acute retroviral infection, viral load (by PCR) should be obtained to confirm HIV status.

CONFIRMATORY TESTING

Tests for viral load (viral DNA or RNA) are typically done as confirmation of a positive screening test or to monitor patients who are known to have positive viral test results. Viral load tests should not be ordered as primary screening tests. Upload source documentation for both the initial and the confirmatory testing results in Rave.

FEDERAL GUIDANCE: GUIDELINES AND RECOMMENDATIONS

Please refer to the following links for more information on federal guidelines and recommendations for testing.

HBV: <http://www.cdc.gov/hepatitis/HBV/TestingChronic.htm>

HCV: <http://www.cdc.gov/hepatitis/hcv/guidelinesc.htm>

HIV: <http://www.cdc.gov/hiv/guidelines/testing.html>

18.4 Intake Calendar

Site Staff Instructions: There is the option for site staff to instruct patients to submit the Intake Calendar electronically (See [Section 7.1b](#)).

(Intake Calendar Page 1)

SWOG Patient ID _____	Patient Initials (L, F, M) _____	SWOG Study # _____
Institution/Affiliate _____ Physician _____		
Instructions for the participant: This is a monthly calendar on which you are to record the number of tablets/pills/capsules you take each day. Be sure you have enough calendars to last until your next appointment. If you develop any side effects from the tablets/pills/capsules, mark this on the calendar on the day you note the effect. Bring your calendars with you each time you have an appointment.		
If you have questions contact: _____ Telephone: _____		
Your study drug is: _____		
Your next appointment is: _____		
Special instructions: Please note the following instructions when taking your an antiviral study drug: 
Take all of your doses as scheduled; do not miss a dose. If you forget a dose, take it as soon as possible, as long as it is at least 12 hours before your next dose is due. If your next dose is due within the next 12 hours, skip the missed dose.The antiviral drug is an oral administration, to be taken as a whole tablet. However, the tablet can be crushed, split or administered via feeding tube with guidance from the treating physician is permitted.Take the antiviral drug with food.The antiviral drug has interactions with other drugs. Tell your doctor you are taking an antiviral drug before starting any new medications.The antiviral drug can cause damage to your liver (called hepatotoxicity). This can cause stomach pain, nausea, unusual tiredness, dark-colored urine, light-colored stools, yellowing of the skin and eyes, loss of appetite, and fever. If you experience these symptoms, contact your doctor immediately.The antiviral drug can cause a build-up of lactic acid in your body. This can cause stomach pain, loss of appetite, diarrhea, fast and shallow breathing, general feeling of discomfort, muscle pain or cramping, unusual sleepiness, or tiredness. If you experience these symptoms, contact your doctor immediately.Talk to your doctor before you stop taking the antiviral drug.		

(Intake Calendar Page 2)

Patient Signature: _____

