8.2 Dose Modifications

General Considerations:

For a more comprehensive list of managing toxicities or management see package insert. Treatment and dose modifications are at the discretion of the treating investigator.

Unacceptable (Grade 3 or greater) and related toxicity necessitating removal from protocol treatment is expected to be rare. Cause of all \geq Grade 3 toxicity should be investigated and changes to protocol treatment made only if toxicity deemed to be related (definite, probable or possible). Antiviral should not be stopped as withdrawal of antiviral may precipitate flare of hepatitis. Instead, patient should be switched to another antiviral that is not associated with that toxicity.

Acute kidney injury has only been reported for TDF. If deemed to be related to TDF, then stop TDF and switch to TAF or ETV.

Lactic acidosis is considered a class effect although data associating it with TDF or TAF are lacking. If deemed to be related, then stop the drug, monitor closely, and when resolved, switch to an alternate antiviral. (48)

Exacerbation of hepatitis associated with discontinuation of antiviral is not related to the antiviral drug itself. This is not applicable to this oncology population where antiviral therapy discontinuation is not expected during anticancer therapy.

TAF-treated patients:

No dosage adjustment of tenofovir alafenamide (TAF) is required in patients with renal impairment with a creatinine clearance ≥ 15 mL/min. Patients with a creatinine clearance < 15 mL/min who are receiving hemodialysis may take the usual dose of TAF (25 mg) on days of dialysis after completion of hemodialysis treatment. TAF is not recommended for patients with creatinine clearance < 15 mL/min who are not receiving hemodialysis.

If a study patient develops creatinine clearance below 15 mL/minute during study participation and is not receiving hemodialysis, then TAF will be discontinued with substitution with an appropriate alternative antiviral as described below at the discretion of the investigator.

TDF-treated patients:

The following guidelines should be used for dose modification of TDF based on creatinine clearance.

Creatinine clearance (mL/min)	Dose
≥ 50	300 mg daily
30-49	300 mg every 48 hours
10-29	300 mg every 72 to 96 hours
Hemodialysis	300 mg every 7 days

ETV-treated patients:

The following guidelines should be used for dose modification of ETV based on creatinine clearance.

Creatinine clearance(mL/min)	Dose
>50	0.5 mg daily

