30-50	0.25 mg daily or 0.5 mg every 48 hours
10-30	0.15 mg daily or 0.5 mg every 72 hours
<10 or hemodialysis or peritoneal dialysis	0.05 mg daily or 0.5 mg every 7 days

Dose Modification Contacts

For treatment or dose modification questions, please contact [name]., M.P.H., [contact], E-mail: [contact] or [name]., [contact] or E-mail: [contact].

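### The Intake Calendar's single 12-hour missed-dose rule suits once-daily dosing but not the extended-interval TDF schedules in Section 8.2 (nor, to a lesser degree, 7-day ETV)

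*Combined protocol and SAP*

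**What the plan says.** Section 18.4 prints one set of instructions for whichever antiviral is written into the blank drug field. A patient who forgets a dose is told to "take it as soon as possible, as long as it is at least 12 hours before your next dose is due". The rule continues: "If your next dose is due within the next 12 hours, skip the missed dose". Section 7.5 makes this calendar compulsory at sites that use the CIRB; other sites may use their own diaries.

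Section 8.2 sets dosing by creatinine clearance (CrCl, mL/min):

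- TDF: "300 mg every 48 hours" at CrCl 30-49, "300 mg every 72 to 96 hours" at 10-29, and "300 mg every 7 days" on hemodialysis. No reduced daily TDF dose is listed.
- ETV: "0.25 mg daily or 0.5 mg every 48 hours" at CrCl 30-50, "0.15 mg daily or 0.5 mg every 72 hours" at 10-30, and "0.05 mg daily or 0.5 mg every 7 days" below 10 or on dialysis.
- TAF: no adjustment at CrCl of 15 or above.

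Section 5.3f requires a creatinine clearance result but sets no minimum, and Sections 7.2 and 7.3 allow a reduced starting dose. Patients on extended intervals are therefore within scope. The readable text contains no other missed-dose rule.

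**The concern.** Section 8.2 lengthens the interval between TDF or ETV doses because the kidneys clear the drug more slowly. The page the patient takes home then allows that interval to shrink to 12 hours after a forgotten dose. Because it gives a definite answer, nothing prompts the patient to call first. The matter is most relevant for TDF: Section 8.2 associates acute kidney injury with that drug alone among the three, and a patient with CrCl below 50 has no daily TDF alternative. What is at stake is a short, avoidable rise in exposure in renally impaired patients.

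**Working it through.** The plan gives no figure on this point, so there is none to reproduce.

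**Inputs.** The minimum gap g = 12 h is from Section 18.4. The intervals τ = 24, 48, 72, 96 and 168 h are from Section 8.2. The half-lives are about 17 h for tenofovir (Section 3.3) and 128-149 h for entecavir (Section 3.1). The documents do not say that the 17 h figure applies in renal impairment, so 34 h and 68 h are added as assumptions.

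**Step 1: spacing.** The gap as a share of the interval is 12/τ: 50% (daily), 25% (48 h), 16.7% (72 h), 12.5% (96 h), 7.1% (7 days). To reach the 12 h gap, the dose must be τ − 12 h late: 36, 60, 84 or 156 h on the non-daily schedules. The preceding gap is 2τ − 12 h, so two intervals still contain the planned number of doses.

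**Step 2: peak.** Assume one compartment, instant absorption, steady state before the miss, a late dose g hours before the next scheduled one, and no modelling of removal by dialysis. Let k = ln 2 / half-life and r = exp(−kτ). In single-dose units the usual steady-state peak is 1/(1 − r). The peak after the late dose and the next scheduled dose is 1 + exp(−kg) + r²/(1 − r). Dividing the second by the first:

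ratio = 1 + (1 − r)(exp(−kg) − r).

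TDF every 48 h at 17 h: r = 0.1413 and exp(−12k) = 0.6131, so the ratio is 1 + 0.8587 × 0.4718 = 1.405.

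ETV every 7 days at 128 h: r = 0.4026 and exp(−12k) = 0.9371, so the ratio is 1 + 0.5974 × 0.5345 = 1.319.

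Adding up the individual doses directly gives the same values, and no later peak is higher.

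| Interval | TDF 17 h | TDF 34 h (assumed) | TDF 68 h (assumed) | ETV 128-149 h | Highest at any half-life |
|---|---|---|---|---|---|
| 24 h | 1.15 | 1.07 | 1.02 | 1.01 | 1.20 |
| 48 h | 1.41 | 1.25 | 1.11 | 1.03-1.04 | 1.42 |
| 72 h | 1.53 | 1.43 | 1.21 | 1.07-1.08 | 1.53 |
| 96 h | 1.58 | 1.55 | 1.32 | not used | 1.61 |
| 7 days | 1.61 | 1.73 | 1.58 | 1.26-1.32 | 1.73 |

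The 1.20 for daily dosing is the most the printed rule can produce on the schedule it suits, and it is a fair yardstick. At 17 h, every non-daily TDF schedule exceeds it. At an assumed 68 h, the 48 h schedule does not and the 72 h schedule barely does. ETV every 48 or 72 h stays well below it; 7-day ETV exceeds it modestly.

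**Step 3: absolute level for TDF, in single-dose units.** A daily patient at 17 h has a usual peak of 1.602. After a dose 12 h late, which the rule allows, the peak is 1.148 × 1.602 = 1.84. The late peaks on the non-daily schedules at 17 h are 1.61-1.64, which is lower. At an assumed 34 h they are 1.78-2.01, or 3% below to 9% above 1.84. At an assumed 68 h they are 1.93-2.86, but the on-time peak of the 48 h schedule is then already 2.58.

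**Step 4: a less extreme lapse.** If the dose is only 24 h late, the gap is τ − 24 h. The highest ratio at any half-life is then 1.20, 1.11, 1.08 and 1.04 for 48 h, 72 h, 96 h and 7 days. None exceeds the daily yardstick.

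**The case against.** The strongest reply is that no consequence is shown. The documents give no toxicity threshold, the rise happens once, it does not accumulate, and the dose over two intervals is unchanged. The worst case needs a patient to be days late, although the page asks for the missed dose as early as possible. All of this stands, and it is why the point is minor.

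Four stronger readings are tempting, and the documents do not support them:

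- *The calendar contradicts Section 8.2.* It does not, since Section 8.2 has no missed-dose rule. This is a poor fit for a subgroup.
- *The falling share of the interval (25% down to 7%) measures excess exposure.* It does not. At 17 h the 7-day schedule has the smallest share, yet its absolute late peak (1.61) is no higher than that of the 48 h schedule (1.64).
- *TDF patients are exposed to harmful levels.* At the only half-life the protocol gives, their late peak is below that of a late daily dose.
- *ETV is affected as much as TDF.* The 48 h and 72 h ETV schedules show almost no effect, and every ETV renal band has a daily option.

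A permissive rule can also be defended. Section 8.2 warns that stopping the antiviral may bring on a hepatitis flare, so taking a late dose may be better than skipping it. That argues against a fixed stricter cut-off, such as half the interval, but not against asking the patient to call.

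Safeguards exist too: investigator discretion, the package insert, a contact line on the page, and calendar and creatinine checks at on-treatment visits. They reduce the risk. Calendar review, however, comes after the dose has been taken, and the printed rule gives no reason to use the contact line.

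**Conclusion.** The point holds as a minor misfit in a patient-facing instruction. It chiefly concerns TDF patients with CrCl below 50 or on hemodialysis and, to a lesser degree, patients on 7-day ETV. The worst-case one-off peak for TDF is about 1.4-1.6 times the patient's own steady-state peak at 17 h, and about 1.1-1.7 times over assumed half-lives of 34-68 h. These sizes rest on the simple model above.

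The group is narrow. TAF is unadjusted down to CrCl 15, ETV can be given daily, and Arms 2 and 3 start drug only after reactivation. The documents do not state how many patients are affected. The second page of the calendar is not readable in the available text, and nothing is claimed about it. No clinical harm is shown, and no endpoint, power figure or analysis changes.

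**What to change.** In Section 18.4, limit the 12-hour line to patients who take the drug once daily, and add: *If you do not take your drug every day, call the study site before taking a missed dose.* This leaves the choice between a late dose and a skipped one to the investigator and introduces no new pharmacological rule. The cost is one revised patient page with its IRB approval and an occasional call to the site. Visits, data collection and analysis are unaffected.

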3.1 Entecavir (ETV)

a. PHARMACOLOGY

Mechanism of Action:

Entecavir is a guanosine nucleoside analogue. The phosphorylated active form inhibits the activity of hepatitis B virus (HBV) polymerase in base priming, reverse transcription of the negative strand pregenomic messenger RNA, and synthesis of the positive strand of HBV DNA.

b. PHARMACOKINETICS

1. Absorption:

The peak plasma concentration (C_{max}) of entecavir is achieved in 0.5 to 1.5 hours at doses ranging between 0.1 and 1 mg, and the steady state is achieved in 6 to 10 days. Both C_{max} and area under the concentration-time curve (AUC) at steady state increases proportionally to increasing doses of entecavir. The oral tablet and the oral solution have a bioavailability ratio of 1:1 and may be used interchangeably.

Co-administration of entecavir with food has been shown to delay absorption, decrease C_{max} by 44 to 46%, and decrease AUC by 18 to 20%. Entecavir should be administered at least 2 hours before or after a meal.

2. Distribution:

Pharmacokinetic studies have shown that entecavir distributes extensively into tissues and have an approximate protein binding of 13%.

3. Metabolism:

Entecavir is not metabolized by the cytochrome P450 enzymes, and it does not inhibit or induce the P450 enzymes.

4. Elimination:

Entecavir is mainly eliminated by the kidneys as 62 to 73% unchanged drug through glomerular filtration and net tubular secretion. The half-life of entecavir is approximately 128 to 149 hours, and the renal clearance ranges between 360 to 471 mL/min.

c. ADVERSE EFFECTS

1. Possible Side Effects of *Entecavir*:

Refer to the current FDA-approved package insert for the most comprehensive and up to date information on adverse reactions.

Adverse effects reported in > 10% of subjects treated with entecavir include elevated alanine aminotransferases.

Adverse effects reported in 1% to 10% of subjects include: headache, fatigue, skin rash, hematuria, glycosuria, hyperglycemia, abdominal pain, nausea, vomiting, diarrhea, unpleasant taste, elevated serum lipase, bilirubin, and creatinine.

Serious adverse effects reported in < 1% of subjects include: anaphylactoid shock, hepatomegaly with steatosis, lactic acidosis, macular edema, and thrombocytopenia.

2. Pregnancy and Lactation:

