3.2 Tenofovir alafenamide (TAF)

a. PHARMACOLOGY

Mechanism of Action: Tenofovir alafenamide (TAF) is an antiviral drug against the hepatitis B virus. It is a phosphonamidite prodrug that is converted intracellularly by hydrolysis to tenofovir, and then phosphorylated into active tenofovir diphosphate. The active moiety inhibits replication of hepatitis B virus (HBV) by incorporating into the viral DNA by HBV reverse transcriptase, thus resulting in DNA chain termination.

b. PHARMACOKINETICS

1. Absorption: There is an increased systemic exposure when taking with food. After administration of tenofovir alafenamide with a high-fat meal (800 kcal, 50% fat), mean AUC increased by 65% (range 51 to 81%).
2. Distribution: TAF is 80% bound to plasma proteins.
3. Metabolism: TAF is extensively metabolized in the liver, primarily by carboxyesterase 1 and minimally by CYP3A. TAF is metabolized by cathepsin A in peripheral blood mononuclear cells. Over 80% of TAF is metabolized to tenofovir, the active major metabolite.
4. Elimination: Kidney (Less than 1%); Feces (31.7%); Elimination Half-life (0.51 hours).

c. ADVERSE EFFECTS

1. Possible Side Effects of tenofovir alafenamide (TAF):

Refer to the current FDA-approved package insert for the most comprehensive and up to date information on adverse reactions.

Adverse effects reported in 1% to 10% of subjects treated with TAF include the following:

CNS: headache (9%), fatigue (6%)
Endocrine & metabolic: increased LDL cholesterol (4%), glycosuria, increased amylase
Gastrointestinal: abdominal pain (7%), nausea (5%)
Hepatic: increased serum ALT, increase serum AST
Neuromuscular & skeletal: decrease bone mineral density (3% to 6%), back pain (5%), increased serum creatine phosphokinase
Respiratory: cough (6%)

2. Pregnancy and Lactation: There are no human data on the use of tenofovir alafenamide (TAF) in pregnant women to inform drug-associated risks of adverse fetal developmental outcome. The background risk of major birth defects and miscarriage for the indicated population is unknown.

It is not known whether TAF and its metabolites are present in human breast milk, affect human milk production, or have effects on the breastfed infant.

The developmental and health benefits of breastfeeding should be considered along with the mother's clinical need for TAF and any potential adverse effects on the breastfed infant from TAF or from the underlying maternal condition.

Drug Interactions:

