Concomitant administration of TAF with carbamazepine, oxcarbazepine, phenobarbital, phenytoin, rifabutin, rifampin, rifapentine, St. John's Wort, and inducers or inhibitors of P-gp may alter the pharmacokinetic or pharmacodynamics properties of TAF. Coadministration of TAF with drugs that reduce renal function or compete for active tubular secretion may also alter the pharmacokinetic or pharmacodynamics properties of TAF. See [Section 7.1](#) for details.

d. DOSING & ADMINISTRATION

See [Section 7.0](#) Treatment Plan

TAF has oral route of administration, intended to be taken as a whole tablet.

e. HOW SUPPLIED

TAF is commercially available and will not be supplied. Refer to the current FDA-approved package insert for the most comprehensive and up to date information.

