3.3 Tenofovir disoproxil fumarate (TDF)

a. PHARMACOLOGY

Mechanism of Action: tenofovir disoproxil fumarate (TDF) is a reverse transcriptase inhibitor and an analog of adenosine 5'-monophosphate. TDF first undergoes hydrolytic conversion to tenofovir and then subsequent phosphorylation to its active form, tenofovir diphosphate (TFV-DP). TFV-DP inhibits the activity of hepatitis B virus reverse transcriptase (HBV RT) by competing with the natural substrate deoxyadenosine 5'-triphosphate and acting as an obligate DNA chain terminator. HBV viral replication is thereby inhibited. TFV-DP also inhibits human immunodeficiency virus type 1 (HIV-1) reverse transcriptase.

b. PHARMACOKINETICS

1. Absorption: In the fasted state, the bioavailability of TDF is approximately 25% and C_{max} occurs approximately 1 hour after administration. Addition of a high-fat meal increases AUC by approximately 40%, and food delays C_{max} by approximately 1 hour. However, these effects have not been deemed to be clinically significant and doses may be given with or without food.
2. Distribution: Tenofovir binds to less than 7.2% of serum proteins. Volume of distribution is 1.2 to 1.3 L/kg.
3. Metabolism: TDF is converted intracellularly by hydrolysis to tenofovir, which is then phosphorylated to active tenofovir diphosphate. Neither TDF nor tenofovir are substrates of CYP enzymes.
4. Elimination: TDF is eliminated by a combination of glomerular filtration and active tubular secretion, with 32% excreted as unchanged drug after oral administration. The terminal elimination half-life of tenofovir is approximately 17 hours.

c. ADVERSE EFFECTS

1. Possible side effects of tenofovir disoproxil fumarate:

Refer to the current FDA-approved package insert for the most comprehensive and up to date information on adverse reactions.

Adverse effects reported in > 20% of subjects treated with TDF include: hypercholesterolemia, abdominal pain, nausea, decreased bone mineral density

Adverse effects reported in 4% to 20% of subjects include: insomnia, headache, pain, back pain, arthralgia, myalgia, dizziness, depression, anxiety, skin rash, pruritus, diarrhea, flatulence, vomiting, increased creatine phosphokinase, increased serum ALT/AST, increased serum amylase, increased serum creatinine, renal failure, fever, fatigue, peripheral neuropathy, sinusitis, upper respiratory tract infections

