7.2 Cohort 1 - Chronic HBV Anti-Viral Treatment

a. Arm 1: Prophylactic Anti-Viral Therapy

The treating investigator and patient will choose the appropriate anti-viral therapy from one of the three anti-viral therapies below. Patients may initiate anti-viral therapy with a reduced dose based on creatinine clearance (see Dose Modifications, [Section 8.2](#))

Start anti-HBV treatment before anti-cancer therapy or up to 42 days after initial anti-cancer therapy. Continue anti-HBV treatment for 6 months after last dose of anti-cancer therapy or for up to 24 months after registration, whichever occurs first.

Agent	Dose	Route	Start Day	Schedule
Tenofovir alafenamide (TAF)	25 mg ^A	PO ^B	As soon as possible after registration; before or up to 42 days after initial dose of anti-cancer therapy	Daily for up to 6 months after the last dose of anti-cancer therapy or maximum of 24 months ^C
Tenofovir disoproxil fumarate (TDF)	300mg PO		As soon as possible after registration; before the last dose or up to 42 days after initial dose of anti-cancer therapy	Daily for up to 6 months after the last dose of anti-cancer therapy or Maximum of 24 months

Entecavir (ETV)	0.5mg	As soon as possible after registration; before the last dose or up to 42 days after initial dose of anti-cancer therapy or anti-cancer therapy.	Daily for up to 6 months after the last dose of anti-cancer therapy or Maximum of 24 months.
--------------------	-------	---	--

^A In patients taking carbamazepine the TAF dose will be increased to 50 mg daily.

^B See dosage administration details in [Section 3.1d](#).

^C Note: Chronic HBV patients should not abruptly stop antiviral therapy after 24 months. Please see [Section 8.2](#) for details on cessation of anti-HBV therapy in chronic HBV patients.

b. Arm 2: Upon Indication Anti-Viral Therapy

The treating investigator and patient will choose the appropriate anti-viral therapy from one of the three anti-viral therapies below. Patients may initiate anti-viral therapy with a reduced dose based on creatinine clearance (see Dose Modifications, [Section 8.2](#)).

Monitor ALT at least every 4 weeks (+/- 2 weeks) as part of trial monitoring for the first 24 weeks, then every 8 weeks thereafter. If hepatitis flare occurs (see definition for hepatitis flare in [Section 10.2b](#)), then obtain an HBV DNA test per usual care. Start anti-HBV therapy if HBV reactivation occurs.

Agent	Dose	Route	Start Day	Schedule

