7.5 Drug Compliance Documentation

Drug compliance will be recorded by patients in the Intake Calendar (see [Appendix 18.3](#)). Institutional CRAs will review and ascertain patient adherence with protocol therapy at the end of treatment. Calendar should be kept in the patient's research chart. Sites utilizing the CIRB must use the Intake Calendar provided. Sites not utilizing the CIRB may utilize institutional pill diaries or other source documentation in place of the Intake Calendar at the discretion of the treating physician.

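### The patient Intake Calendar tells everyone to take the antiviral with food, which contradicts Section 3.1 for entecavir

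*Combined protocol and SAP*

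**What the plan says.** Section 18.4 contains one calendar for all protocol antivirals. The drug name is a blank for the site to fill in, and the special instructions below it are fixed print. One of them reads "Take the antiviral drug with food". Section 7.5 adds "Sites utilizing the CIRB must use the Intake Calendar provided"; sites outside the CIRB may use their own diaries or other source documents.

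The drug sections differ by agent:

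- **Entecavir (3.1b):** food delays absorption, lowers Cmax by 44 to 46% "and decrease AUC by 18 to 20"%. The instruction is "Entecavir should be administered at least 2 hours before or after a meal".
- **TAF (3.2b, 3.2d):** "There is an increased systemic exposure when taking with food". No food instruction follows. The dosing paragraph says only "TAF has oral route of administration, intended to be taken as a whole tablet".
- **TDF (3.3b):** "doses may be given with or without food".

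Entecavir 0.5 mg is one of the three options in Arm 1 (7.2a) from the start, and in Arms 2 and 3 (7.2b, 7.3a) once reactivation occurs.

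**The concern.** The calendar is the document the patient keeps and follows at home. For entecavir its food line is the reverse of the protocol's own administration rule. Dosing is daily and can run for up to 24 months after registration, so the wrong instruction is repeated rather than given once.

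Arm 1 is the most exposed, because prophylactic antiviral therapy is the experimental treatment there and every patient is due to start it. Some patients are also steered towards entecavir. Sections 5.2 and 7.1a offer entecavir or TDF to those on drugs that interact with TAF, and Section 8.2 offers TAF or entecavir after kidney injury attributed to TDF.

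What is at stake is correct dosing of one permitted study drug. The documents give no link from the lower exposure to viral suppression, reactivation, liver failure or power.

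**Working it through.** **Step 1. Compare the texts.**

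| Drug | Drug section | Calendar line (18.4) | Conflict? |
|---|---|---|---|
| Entecavir | Away from meals by at least 2 hours (3.1b) | With food | Yes, opposite |
| TAF | Exposure rises with food; no instruction (3.2b, 3.2d) | With food | No |
| TDF | Food does not matter (3.3b) | With food | No |

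**Step 2. Look for text that resolves the conflict.** Section 3.1d only points to Section 7.0. The entecavir rows for Arms 2 and 3 carry no meal timing, and none is visible in the Arm 1 row. Package-insert referrals appear in 3.1c (adverse reactions), 3.1e (supply) and 7.1a (concomitant medications). They address the site and leave the patient's form unchanged. Nothing resolves the conflict.

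**Step 3. Size of the exposure loss, from 3.1b.** Relative to dosing away from food:

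- AUC falls to between 100 − 20 = 80% and 100 − 18 = 82%.
- Cmax falls to between 100 − 46 = 54% and 100 − 44 = 56%.

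**Step 4. Patients who could receive the instruction.** Inputs: 111 per arm (11.1); one-year reactivation of 20% on the standard arm and 10% on the experimental arm (11.2). Arm 2 is the standard arm of Cohort 1 and Arm 3 the experimental arm of Cohort 2. Assume that every reactivation in Arms 2 and 3 leads to a protocol antiviral.

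- Arm 1: 111
- Arm 2: 0.20 × 111 = 22.2
- Arm 3: 0.10 × 111 = 11.1
- Total: 111 + 22.2 + 11.1 = 144.3
- If Arm 3 also reaches 20%: 111 + 22.2 + 22.2 = 155.4

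The share choosing entecavir is not in the documents, so it is shown as a range of assumptions:

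| Assumed entecavir share | Arm 1 | Arm 2 | Arm 3 | Total | Total if Arm 3 is at 20% |
|---|---|---|---|---|---|
| 10% | 11.1 | 2.2 | 1.1 | 14.4 | 15.5 |
| One third | 37.0 | 7.4 | 3.7 | 48.1 | 51.8 |
| 50% | 55.5 | 11.1 | 5.6 | 72.1 | 77.7 |

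These counts cover one year. They are not adjusted for the 10% dropout in 11.1, for reactivation after year 1, or for sites using other diaries. Arm 4 is left out.

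**Step 5. A related cross-reference.** Footnote B in 7.2 and 7.3 is attached to the TAF rows and reads "See dosage administration details in" Section 3.1d. That is the entecavir dosing paragraph; TAF dosing is in 3.2d.

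**The case against.** The best opposing case accepts the conflict but calls it a small wording fault in an appendix form. The investigator has the correct rule in 3.1b, the form has a space for a contact for questions, and no effect on any endpoint is shown. Correcting the one calendar line would be enough, and the patient counts rest on entecavir shares the protocol does not give.

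Much of this is fair as a limit on size:

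- **Counts.** They are illustrative, and they assume that the patient follows the form rather than any advice from the site.
- **Arms 2 and 3.** These figures are best read as upper values. Under 7.2b and 7.3a a hepatitis flare prompts the HBV DNA test, and Section 18.1 uses banked specimens to identify reactivation retrospectively. Reactivation without a flare may go untreated at the time.
- **Arm 4.** Section 9.3 lists calendar review for Arm 4 if an antiviral was started per protocol, and 7.3b allows any approved agent there. Its contribution cannot be settled from the text.
- **Arm 1 table.** The entecavir row is damaged in the extracted text, so the absence of meal timing there should be confirmed in the source file. The Arm 2 and 3 rows are clear.
- **Footnote B and the TAF sentence.** Both are tidying, and the finding does not depend on them.

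None of this removes the contradiction. A correct rule in the pharmacology section does not help a patient holding a form that says the reverse. If the site does counsel correctly, the patient then has two conflicting instructions, one of them on the official study form.

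**Conclusion.** The concern holds: for entecavir, the calendar's food line is wrong as written, judged by the protocol's own text. It should be corrected. A patient on entecavir who follows it would, by the figures in 3.1b, have AUC 18 to 20% lower and Cmax 44 to 46% lower.

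The reach is limited to patients who take entecavir and are given this calendar. For Arms 1 to 3 that is about 14, 48 or 72 patients in the first year at assumed shares of 10%, one third or 50%. Arm 1 accounts for about 11, 37 or 56 of them. Use of other diaries at non-CIRB sites would lower these figures. No clinical consequence or loss of power is established.

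**What to change.** - **Section 18.4:** replace the single food line with three options, of which the site ticks one. Entecavir: at least 2 hours before or after a meal. TDF: with or without food. TAF: with food, as the calendar now says. This alone removes the contradiction.
- **Sections 7.2 and 7.3:** add the meal timing to each entecavir row, so that sites see it where they look up the dose.
- **Section 3.2d:** add a sentence stating the TAF food instruction, so that the calendar line has a source in the drug section.
- **Footnote B in 7.2 and 7.3:** change the reference from 3.1d to 3.2d.

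The cost is one revised calendar line, one sentence, a phrase per entecavir row and a corrected cross-reference, all through a routine amendment. Sample size, endpoints and analysis are unchanged.
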